## **8.5 Analysis of secondary variables**

### **8.5.1 Efficacy variables**

Kaplan-Meier estimates will be presented for time to relapse.

Continuous endpoints (steroid tapering, VAS scores, BDCAF scores) will be summarized by mean, standard deviation, median, median, interquartile range, minimum and maximum.

Differences between pre-treatment and post-treatment values will be analysed by the non-parametric Wilcoxon signed rank test at the 0.05 level of significance.

Correlations between the different parameters will be explored by Spearman's rank correlation coefficient.

Categorical variables will be summarized by absolute frequencies and percentages.

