## 2.2 Secondary objectives

### Secondary endpoints:

#### General :

Overall disease activity measures (BDCAF-Behçet's Disease Current Activity Form)

Reduced need for corticosteroid treatment (reduction of corticosteroid dosage)

Course of other BD-related manifestations

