### **5.9.4 Steroid Tapering**

Prednisolone dosage should be 20 mg or less at baseline, and it should not be increased during the trial.

At the end of Day 30, complete responders begin to decrease the steroid doses. Tapering target will be 2,5 mg for every 2 weeks. At Day 120, patients expected to use prednisolone no more than 5 mg / day.

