### **8.4.2 Statistical model, hypothesis, and method of analysis**

To claim the efficacy of canakinumab on the resolution of attacks, at least 50% response will be aimed in at least 50% of the patients.

All parameters will be compared with baseline values. Complete / Partial / Non responders definitions can be seen in efficacy assessment section.

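### After Day 30 the Wilcoxon test of steroid dose cannot show reduced steroid need, because the protocol itself instructs the fall being tested

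*Combined protocol and SAP*

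**What the plan says.** The secondary endpoint in Section 2.2 reads "Reduced need for corticosteroid treatment (reduction of corticosteroid dosage", so a lower dose is taken as the measure of lower need. Section 8.5.1 begins its list of continuous variables with steroid dose: "Continuous endpoints (steroid tapering, VAS scores, BDCAF scores) will be summarized by mean". The next sentence there sets the test: "Differences between pre-treatment and post-treatment values will be analysed by the non-parametric Wilcoxon signed rank test at the 0.05 level of significance". Section 8.4.2 adds "All parameters will be compared with baseline values". Section 8.6 places analyses at Days 30, 90, 180 and 360.

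Section 5.9.4 sets the dose itself: "Prednisolone dosage should be 20 mg or less at baseline, and it should not be increased during the trial". It continues "At the end of Day 30, complete responders begin to decrease the steroid doses" and "Tapering target will be 2,5 mg for every 2 weeks", and expects at most 5 mg/day at Day 120. Sections 3.1 and 5.5.5 drop non-responding or deteriorating patients at the first-month evaluation. Section 3.1 has one arm, and Section 8.7 gives 10 patients without a calculation.

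Section 5.5.6, however, allows rescue with raised prednisolone or intravenous pulses. Section 5.5.8 prohibits steroid above a stated limit during the study, and Section 5.5.9 requires study drug to stop when a prohibited medication is used.

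**The concern.** The signed rank test asks whether changes in dose are symmetric about zero. That is a useful question for a measured outcome such as a VAS or BDCAF score. Steroid dose after Day 30 is different, because the protocol prescribes its direction for complete responders and says of the dose that "it should not be increased during the trial". The patients most likely to need more steroid are removed at month 1, and no comparison group shows what the same taper would do without canakinumab.

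Rejecting the null then mainly shows that the instruction was carried out in enough patients. Need is reduced only if the patient stays well on the lower dose, and the test does not look at that. At stake is the interpretation of a named secondary endpoint: a p-value below 0.05 could be read as steroid sparing when it need not reflect any.

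**Working it through.** **Inputs.** Baseline cap 20 mg, taper 2.5 mg per 2 weeks from Day 30, at most 5 mg/day expected at Day 120 (Section 5.9.4). Level 0.05 (Section 8.5.1). Analyses at Days 30, 90, 180 and 360 (Section 8.6). N = 10 (Section 8.7). The plan does not state sidedness, exact or approximate p, or the handling of zeros. I assume a two-sided exact test with zeros dropped.

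**1. The plan's own figure.** Dose at day t from baseline b is max(0, b − 2.5 × floor((t − 30)/14)). From 20 mg:
- Day 30: no step yet, 20 mg.
- Day 90: floor(60/14) = 4 steps, 20 − 10 = 10 mg.
- Day 120: floor(90/14) = 6 steps, 20 − 15 = 5 mg (reached on Day 30 + 6 × 14 = 114).
- Day 180: floor(150/14) = 10 steps, 0 mg if the rate continues.

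The Day 120 figure reproduces. Any tapering patient with a non-zero baseline dose is below baseline at Days 90, 180 and 360 by instruction. At Day 30 no fall has yet been ordered.

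**2. The p-value from the taper alone.** If all n non-zero changes are falls, exact two-sided p = 2/2^n:

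| n falling | p |
|---|---|
| 4 | 2/16 = 0.125 |
| 5 | 2/32 = 0.0625 |
| 6 | 2/64 = 0.031 |
| 7 | 2/128 = 0.016 |
| 10 | 2/1024 = 0.002 |

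Six tapering and four unchanged patients give 0.031; five and five give 0.0625. Other implementations move the threshold: with n = 5, the one-sided exact p is 0.031 and the normal approximation without continuity correction (no ties) gives 0.043.

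**3. How likely six are.** The documents give neither the complete-response rate r nor the share s on steroid at baseline, so both are assumed. With X ~ Binomial(10, r × s), P(X ≥ 6) is:

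| r | s = 1 | s = 0.8 |
|---|---|---|
| 0.5 | 0.38 | 0.17 |
| 0.6 | 0.63 | 0.33 |
| 0.7 | 0.85 | 0.53 |

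**4. One rescued patient.** A fall cannot exceed the 20 mg baseline cap, so a rise above 20 mg takes the largest rank. With nine falls and one such rise, the rank sum of rises is 10. There are 43 of 1,024 sign patterns with a rank sum of 10 or less, so p = 2 × 43/1024 = 0.084. If that patient is left out, p = 2/2^9 = 0.0039. With seven falls and one largest-rank rise, p = 2 × 25/256 = 0.195; without that patient, 2/2^7 = 0.016. Section 8 does not say which applies.

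**The case against.** A reader might infer something stronger: that dose can only fall in this trial, whatever the drug does, so that p < 0.05 is automatic. The documents do not support that.

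- The start of the taper is ordered for complete responders only. The rate is a target and the Day 120 dose an expectation. With no complete responders no fall is ordered, so the fall depends on response.
- Section 5.5.6 allows increases as rescue, so a positive change can occur within the protocol.
- Leavers are not simply lost. Section 5.5.10 analyses data up to discontinuation, Section 5.7 schedules a visit after the last dose with the final-visit assessments, and Section 8.1 defines an intent-to-treat set of all treated patients.
- Five tapering patients give 0.0625, and at Day 30 nothing has been tapered by instruction.

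All of this stands and limits the claim. It does not rescue the test. To the extent that the fall reflects response, it repeats the Day 30 complete-response percentage already listed in Section 8.4.1. The openness about rescue and leavers adds a second way in which the p-value depends on something other than need.

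Two further points are fair. Section 8.1 calls the study exploratory and not powered, and the efficacy claim rule in Section 8.4.2 concerns resolution of attacks, so this test carries limited weight. Yet Section 8.5.1 still fixes a 0.05 level. Section 8.4.1 also already lists a percentage with appropriate tapering, but does not define it. Finally, a bare 5 mg criterion would itself be shaped by the taper rule and could count partial responders as failures although they have no taper instruction. The fix therefore adds clinical conditions and a breakdown by response.

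**Conclusion.** The point holds in a conditional form. After Day 30 the Wilcoxon test of dose cannot by itself show reduced steroid need. If at least six patients on steroid at baseline follow the taper and no rescue increase enters the analysis, the instruction alone gives an exact two-sided p between 0.031 (n = 6) and 0.002 (n = 10). With five or fewer falls, that test cannot reach 0.05. Where one of ten patients is rescued with a large increase, an unstated choice moves p between 0.084 and 0.0039.

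This rests on a two-sided exact test with zeros dropped, and on tapering patients having a non-zero baseline dose. The chance of reaching six depends on two rates that the documents do not give. It does not follow that significance is guaranteed or that dose cannot rise. The problem concerns steroid dose, not the Wilcoxon tests of VAS or BDCAF. It should be changed, because the endpoint claims need and the repair is cheap.

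**What to change.** In Section 8.5.1, remove steroid dose from the Wilcoxon test. Summarise it descriptively at the planned analysis days, with individual dose-time plots that mark attacks, rescue and withdrawal.

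For the secondary endpoint in Section 2.2, and as the definition of appropriate tapering in Section 8.4.1, report n/N with an exact confidence interval:
- **Denominator:** intent-to-treat patients above 5 mg/day at baseline.
- **Success:** at or below the plan's own 5 mg/day figure at Day 120, with no attack, steroid rescue or dose re-increase up to an analysis day stated in advance (for example Day 180).
- **Failures:** all others, including rescued and dropped patients.
- **Display:** also by Day 30 response category, because partial responders have no taper instruction.

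Sections 5.5.6, 5.5.8, 5.5.9 and 5.9.4 conflict on whether steroid may be increased and what follows if it is. They must be reconciled so that rescue and re-increase can be coded in one way.

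The analysis change needs new wording only, since the visit schedule already records steroid use and attacks at every visit. The price is the loss of a p-value likely to look favourable, and an interval that will be wide with 10 patients or fewer.

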**Partial response** will be defined as clinical and laboratory improvement based on observations of an improvement between 20-49% according to patient's and physician's global assessments by using VAS, 20-49% reduction in CRP values; along with stable or less than 20% reduced aneurym size in patients with arterial involvement, and stable or less than 20% reduced calf swelling in patients with lower extremity thrombosis.

**Non-response** will be defined as observing no or less than 20% clinical improvement by patient's and physician's global VAS or worsening of clinical findings, no change or increase in acute phase response, increase in aneurysm size for patients with arterial involvement or progression of venous thrombosis in patients with venous involvement.

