### 3 Investigational plan

#### 3.1 Study design

The study will be conducted as an exploratory open-label pilot trial. There will be only one treatment arm. The improvement will be evaluated in comparison to the findings recorded at the baseline.

Figure 3-1 Study design

Approximately 10 subjects aged 18 to 60 years, who sign an informed consent and meet all inclusion and exclusion criteria in the screening period will enter into the study. The first dose of canakinumab will be administered as 300 mg IV.

At the end of the first month, an analysis will be conducted to assess the complete, partial, and non-responders to canakinumab treatment by physician.

Partial responders will be able to take the 2nd canakinumab dose as 300 mg IV infusion at the first month then will continue the canakinumab treatment with 150 mg IV infusions at monthly intervals for 4 times. The complete responders will continue the canakinumab treatment with 150 mg IV infusions at monthly intervals for 5 times. Non-responder or deteriorating patients will be dropped from the study at the first month evaluations.

At month 6, the patients will be able to switch to SC injections or continue as IV infusions of 150 mg canakinumab for additional 6 monthly administrations. Non-responder or deteriorating patients will be dropped from the study at the first month evaluations.

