### **5.9.3 Overall Disease Activity Measures**

Using Behcet Disease Current Activity Form (BDCAF) to collect general information about the disease course and progress. The patient will fill the form starting from baseline till the end of the study in every treatment day. The scores will be analysed at Day 30, 90, 180 and 360.

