### **8 Data analysis**

#### **8.1 Analysis sets**

Investigators will enter the information required by the protocol into the Novartis Case Report Forms (CRFs). Non-obvious errors or omissions will be entered on Data Query Forms, which will be returned to the investigational site for resolution.

The data from all centers will be pooled and summarized with respect to demographic and baseline characteristics and efficacy and safety observations. [REDACTED]

[REDACTED] Data will be presented for the complete intent-to-treat population (all subjects having taken at least one dose of study medication) as well as the per-protocol population (all subjects who completed the study without major protocol deviations). Safety data will be evaluated for the safety population (all subjects having taken at least one dose and who have at least one post-baseline assessment).

Data summaries will be presented.

This trial is an exploratory study, and it is not powered for a statistical analysis. The statistical analyses of the measurements will be performed when possible, and these analysis will be done by the investigators and an independent Contract Research Organization.

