## **8.6 Interim analyses**

There will be statistical analysis at Day 30 , Day 90, Day 180 and Day 360.

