## **8.7 Sample size calculation**

Because of exploratory nature of the study, 10 patients will provide information.

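### From Day 90 on, the pre/post comparisons of BDCAF and VAS can use only patients kept after the Day 30 response rule, so they lean toward improvement and do not describe all dosed patients

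*Combined protocol and SAP*

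**What the plan says.** Five places in the combined protocol and SAP bear on this.

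- **Test.** Section 8.5.1: "Differences between pre-treatment and post-treatment values will be analysed by the non-parametric Wilcoxon signed rank test at the 0.05 level of significance". The variables are named in the same section: "Continuous endpoints (steroid tapering, VAS scores, BDCAF scores) will be summarized by mean". Section 8.4.1 also lists VAS symptom scores and BDCAF change under the primary heading.
- **Times.** Section 8.6: "There will be statistical analysis at Day 30 , Day 90, Day 180 and Day 360". For BDCAF, section 5.9.3 adds: "The scores will be analysed at Day 30, 90, 180 and 360".
- **Removal.** Section 3.1, repeated in 5.5.5: "Non-responder or deteriorating patients will be dropped from the study at the first month evaluations". For vascular patients, section 2.1 defines non-response partly as "observing no or less than 20% clinical improvement by patient's and physician's global VAS or worsening of clinical findings". For neurologic patients the categories rest on clinical, MRI and CSF findings.
- **Population.** Section 8.1: "Data will be presented for the complete intent-to-treat population (all subjects having taken at least one dose of study medication". A per-protocol set of completers is presented as well.
- **Missing values.** Section 5.5.10 says that data up to discontinuation are analysed. Section 5.7 asks for one final-type visit 8 weeks (±1 week) after the last dose. No section says how a dropped patient enters a Day 90, 180 or 360 comparison.

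**The concern.** A patient reaches Day 90 only by having been judged a responder at Day 30. A later change from baseline uses the same baseline as the Day 30 change, so patients with a chance high baseline or a chance good Day 30 tend to be kept, and part of that chance carries into their later change. The signed-rank test assumes changes symmetric about zero when nothing has happened. In patients selected for improvement that need not hold.

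At stake are the longer-term BDCAF and VAS results of an uncontrolled trial of one year's treatment. Three of the four analysis times are affected. With no control arm, nothing else in the trial would reveal the shift. The Day 30 comparison is not affected by this rule.

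**Working it through.** **1. Who has data from Day 90.** A patient dosed only on Day 0 and dropped at month 1 has the 8-week visit at Day 56 ± 7, that is Day 49 to 63. With the ±7-day window of section 5.7, the Day 90 visit starts at Day 83. This assumes no Day 30 dose for such a patient; section 3.1 describes that dose only for responders. So no dropped patient has a scheduled Day 90, 180 or 360 value.

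**2. Benchmark.** The plan's 0.05 is a chosen level, and section 8.7 gives no calculation ("Because of exploratory nature of the study, 10 patients will provide information"), so there is no derived figure to reproduce. Sidedness is not stated; I take two-sided. For the exact signed-rank test:

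- n = 10: 25/1024 = 2.4% in each direction, 4.9% in total.
- n = 6: smallest two-sided p = 2/64 = 0.031.
- n = 5: smallest two-sided p = 2/32 = 0.0625, so rejection is impossible with five or fewer patients.

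**3. Shift in the mean.** Let D30 be the Day 30 change in whatever decides retention, D the later change in the tested score, both with mean 0 and SD 1 in all dosed patients, with correlation r. A patient is kept if D30 < c (negative means improvement). Then

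mean of D in kept patients = −r × φ(c)/Φ(c),

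where φ and Φ are the standard normal density and distribution function.

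- 50% kept (c = 0): φ/Φ = 0.399/0.5 = 0.798. The shift is −0.24 SD (r = 0.3), −0.40 (0.5) and −0.56 (0.7).
- 69% kept (c = 0.5): φ/Φ = 0.352/0.691 = 0.509. The shift is −0.15, −0.25 and −0.36 SD.

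Retention and r are assumptions. If the tested score is itself the retention score, and the three readings are independent with equal variance σ², the shared baseline alone gives r = σ²/(2σ²) = 0.5. For other scores r may be lower.

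**4. Rejection rates.** Simulation of 40,000 trials of 10 patients with no change in the treated population, testing kept patients only with the exact test:

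| Kept | r | In the drug's favour | Against |
|---|---|---|---|
| 50% | 0 | 0.8% | 0.8% |
| 50% | 0.3 | 2.1% | 0.2% |
| 50% | 0.5 | 4.4% | 0.1% |
| 50% | 0.7 | 8.9% | <0.1% |
| 69% | 0 | 1.6% | 1.8% |
| 69% | 0.3 | 3.6% | 0.7% |
| 69% | 0.5 | 6.2% | 0.3% |
| 69% | 0.7 | 10.1% | 0.1% |

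At 60% kept, a smaller run (6,000 trials) gave 5.7% (r = 0.5) and 11.1% (r = 0.7) in favour. Outside this range, for r = 0.3 to 0.7, the favourable rate is 3.6–7.6% at 80% kept and 0.5–2.2% at 31% kept. The rates stay modest at low retention because the test often cannot reject: at 50% kept, at least 6 of 10 remain in only 386/1024 = 37.7% of trials.

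**5. Last value carried forward.** Giving each dropped patient the Day 30 value makes the overall mean (1 − r) × φ(c). At 50% kept and r = 0.5 this is 0.5 × 0.399 = +0.20 SD, toward worsening. The test then rejects in favour in 0.2% of trials and against the drug in 11.9%. Across 50–70% kept, rejection against the drug is about 5–12% at r = 0.5–0.7 and 11–18% at r = 0.3.

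**The case against.** The strongest reply has four parts.

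*The link is often indirect.* BDCAF is in neither disease's response categories, and the neurologic categories name no VAS. The vascular categories use the patient's and physician's global VAS, whereas 8.4.1 and 5.9.5 concern symptom VAS, which the visit schedule lists on a separate row (section 5.9.1 blurs the two). This stands. The link is direct only for global VAS in vascular patients, and r = 0.5–0.7 should not be assumed for every score. In a model on the VAS scale itself (assumed mean 6, SD 2, within-patient correlation 0.3 or 0.6), kept patients' mean VAS change was −0.5 to −1.3 points with no population change, but favourable rejection was only 0–5.7% for VAS and 0–3.5% for BDCAF, because strict retention leaves few patients.

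*The stated 0.05 is not always exceeded.* At 50% kept and r = 0.5, total rejection is 4.4% + 0.1% = 4.5%. This stands too, but nearly all of it falls on one side, and the mean is shifted whether or not a test can run.

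*The timing is partly inferred.* Section 8.5.1 gives no days for the test. Section 5.9.3 fixes days for BDCAF only, 8.6 is generic, and 3.4 names general disease activity but not VAS at months 3 and 6. That retained-only results would carry the intent-to-treat label is likewise a reading of 8.1, not an explicit statement. Stating the days and the set is part of the fix.

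*The trial is exploratory.* Section 8.1 says that it is not powered, and the only efficacy-claim criterion, in 8.4.2, is a response proportion. This limits the consequence. It does not remove a shift in one direction.

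A reader might infer that the later tests will usually come out significant for the drug, or that the efficacy claim itself is undermined. The documents support neither: they give no retention or correlation, and the 8.4.2 criterion does not depend on these tests.

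**Conclusion.** The point holds in limited form. At Days 90, 180 and 360 the BDCAF and VAS comparisons can use only patients retained after the Day 30 response rule, and nothing in the plan reconciles this with presentation for all dosed patients. Where the tested score correlates with the Day 30 criterion, the retained mean overstates improvement and the signed-rank test does not have its nominal properties for the treated population.

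With N = 10 and 50–70% kept, the overstatement is about 0.15–0.24 SD at r = 0.3 and 0.25–0.56 SD at r = 0.5–0.7. Favourable rejection is about 2–4% and 4–11%, against 2.4% for all 10 patients. At r = 0.3 the rejection rate is thus barely raised, if at all, and the problem is mainly the mean. At r = 0 there is no bias. These sizes rest on assumed retention and correlation, normally distributed changes, and a two-sided exact test.

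**What to change.** In section 8.5.1:

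- Make Day 30, in all dosed patients with a value, the time point for the BDCAF and VAS signed-rank tests.
- Present Days 90, 180 and 360 descriptively, without a p-value, under a title such as *patients retained after the Day 30 response rule*, with the number dropped beside each mean.
- Do not label these later results intent-to-treat.
- Do not use last value carried forward as the repair. It replaces a bias toward the drug with one against it.

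The cost is a few sentences and some table titles, with no new data and no change to how patients are managed. The price is that the later scores have no formal test, which is a small loss in an exploratory, unpowered trial.

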### **8.5.2 Safety variables**

The assessment of safety will be based mainly on the frequency of adverse events, which includes all serious adverse events. Adverse events will be summarized by the number and percentage of subjects having any adverse event, having an adverse event in each body system and having each individual adverse event. Any other information collected (e.g. severity or relatedness to study medication) will be listed as appropriate.

Newly occurring notable laboratory values and newly occurring vital sign abnormalities will be tabulated. Listings with abnormalities flagged will be provided

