## Protocol summary

Protocol number	CACZ885NTR01
Title	An open label, exploratory study to establish the efficacy and safety of 1 year Canakinumab treatment in Behçet's Disease Patients with Neurologic or Vascular Involvement
Brief title	Efficacy and Safety of Canakinumab in Behçet's Disease Patients with Neurologic or Vascular Involvement
Sponsor and Clinical Phase	Novartis Phase 2 Exploratory Study
Investigation type	Drug
Study type	An open label Phase 2 Study
Purpose and rationale	Study objective is to evaluate efficacy and safety of canakinumab in neurologic and vascular subtypes of Behçet's disease (BD).
Primary Objective(s)	Primary objective of the study is to evaluate the safety and efficacy of canakinumab on the clinical and inflammatory findings of BD patients with neurologic and vascular involvement.
Secondary Objectives	Secondary objectives include analyses measuring the effects of canakinumab on radiological findings (neurologic and vascular), cerebrospinal fluid (CSF) findings (neurologic), and [REDACTED] [REDACTED] aiming to investigate the biology of inflammatory attacks and their response to IL-1 blockade in parallel with clinical findings.
Study design	The study will be conducted as an exploratory open-label pilot trial. There will be only one treatment arm. The improvement will be evaluated in comparison to the findings recorded at the baseline.
Population	Biologic naïve patients aged over 18 with BD fulfilling the International Study Group (ISG) criteria, who have a recent exacerbation of large-vessel vascular disease and/or parenchymal neurologic disease (within the last month).
Inclusion criteria	
For NBS :1) Patients experiencing an acute exacerbation of parenchymal neurologic disease involving brainstem and/or diencephalic region with in last month.
 
Exacerbation is defined based on the presence of both of the following:
 
 
a. An acute/subacute neurological syndrome including any of hemiparesis, ataxia, dysarthria within the first month
 

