## 5.7 Patient demographics/other baseline characteristics

Patient demographic and baseline characteristic data to be collected on all patients include: date of birth, age, sex, ethnicity, patient referral source, relevant medical history/current medical condition present before signing informed consent. Where possible, diagnoses will be recorded, not symptoms.

Subjects should be seen for all post-baseline visits on the designated day with the allowance of a  $\pm 7$  day window for all visits. Subjects who discontinue study drug before completing the study, and those who prematurely withdraw from the study for any reason, should be scheduled for a visit 8 weeks ( $\pm 1$  week) after their last infusion /injection, at which time all of the assessments listed for the final visit will be performed.

Subjects who discontinue study drug also should return for a last assessment. If they refuse to return for this or are unable to do so, every effort should be made to contact them or a knowledgeable informant by telephone to determine the reason for discontinuation. At a minimum, they will be contacted for safety evaluations during the 30 days following the last dose of study drug, including final contact at the 30-day point. Documentation of attempts to contact the patient should be recorded in the patient record.

Information that will be collected on subjects who are screened but not enrolled includes patient demographics (age, gender, and ethnicity) and primary reason for not continuing.

If a patient discontinues before entering Visit 1, only the demographic information and Screening Log entry with the primary reason for discontinuation should be completed on the CRF. It is not necessary to complete all the required evaluations at the time of discontinuation unless medically indicated.

At screening visit information on age, sex, will be collected. Relevant medical history/current medical conditions, family medical history, will be recorded on the respective CRF page. The following should be recorded on the respective CRF page.

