#### **8.3 Treatments**

The exposure to study drug (number of injections) and duration of exposure (days) will be summarized and listed.

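### Adverse events are summarised only as crude percentages although follow-up runs, by design, from about 8 weeks to about 12 months, so the figure can understate one-year risk

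*Combined protocol and SAP*

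**What the plan says.** Safety is part of the primary objective (section 2), and the title in the protocol summary refers to "efficacy and safety of 1 year Canakinumab treatment".

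For the analysis, section 8.5.2 states: "Adverse events will be summarized by the number and percentage of subjects having any adverse event". The same is done by body system and by individual event. Of the rest it says: "Any other information collected (e.g. severity or relatedness to study medication) will be listed as appropriate". Under section 8.1 the safety population is every dosed patient with any assessment after baseline, so early leavers and completers share one denominator.

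Follow-up is set elsewhere:

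- Section 3.1, repeated in 5.5.5: "Non-responder or deteriorating patients will be dropped from the study at the first month evaluations". Such a patient has had only the Day 0 dose.
- Section 5.7 covers patients who stop the drug early and "those who prematurely withdraw from the study for any reason, should be scheduled for a visit 8 weeks" (plus or minus 1 week) after the last infusion or injection. For those who cannot or will not return, the minimum is safety contact for 30 days after the last dose.
- Section 6.2.2 requires every serious event to be reported up to 30 days after the last dose, and later ones only if a causal link is suspected.
- The assessment schedule takes continuing patients to Day 360.

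Section 8.3 states: "The exposure to study drug (number of injections) and duration of exposure (days) will be summarized and listed". It does not connect exposure to adverse events. Section 8.6 plans analyses at Days 30, 90, 180 and 360 without mentioning adverse events.

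**The concern.** Time under observation differs about sixfold between the two groups (360/56 = 6.4), and which group a patient joins depends on response. This is a rule of the design, not incidental dropout. A crude percentage over the pooled group mixes risk over about 8 weeks with risk over about a year, and nothing in 8.5.2 says which period it describes.

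For relapse the plan does use a method that allows for unequal follow-up: "Kaplan-Meier estimates will be presented for time to relapse". It plans nothing comparable for adverse events.

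A reader who takes the title at its word will read the percentage as the risk over one year of treatment. Events that would have occurred after an early exit are not observed, so under that reading the error, if there is one, is downward. Comparison with other one-year safety data would be affected in the same way.

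**Working it through.** The plan gives no adverse event rate, non-response rate or dropout rate, so there is no stated figure to reproduce. The calculation is a set of scenarios.

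**Inputs from the documents**

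- N = 10 patients, one arm (3.1, 8.7).
- Follow-up of continuing patients: about 360 days (assessment schedule).
- Follow-up of a Day 30 non-responder last dosed on Day 0: 8 weeks = 56 days, with a window of 49 to 63 (5.7). Under the minimum contact it is about 30 days.

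**Assumptions**

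- R = one-year risk of at least one event if a patient were treated and followed for the full period, the same for everyone.
- k = number of patients leaving at Day 30. Section 8.4.2 seeks a response in at least half of the patients, so k up to 5 is compatible with a claim of efficacy.
- f = share of the one-year cumulative hazard that falls within the leaver's follow-up. Under a constant hazard, f = t/360.

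**Formula**

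Risk seen in a leaver: s = 1 − (1 − R)^f.

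Expected crude proportion: [(10 − k) × R + k × s] / 10.

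**Constant hazard, t = 56**

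For R = 50%: s = 1 − 0.5^(56/360) = 10.2%. With k = 2: (8 × 0.50 + 2 × 0.102)/10 = 42.0%.

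| Leaving at Day 30 | Crude %, R = 50% | Crude %, R = 20% | Relative shortfall | Patient-years (360-day years) |
|---|---|---|---|---|
| 0 | 50.0 | 20.0 | 0 | 10.0 |
| 1 | 46.0 | 18.3 | about 8% | 9.2 |
| 2 | 42.0 | 16.7 | 16–17% | 8.3 |
| 3 | 38.1 | 15.0 | 24–25% | 7.5 |
| 5 | 30.1 | 11.7 | 40–42% | 5.8 |

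The last column is [(10 − k) × 360 + k × 56]/360.

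**Shorter follow-up of leavers.** If only the 30-day minimum contact is achieved and R = 50%, the crude figure is 41.1% with 2 leaving and 27.8% with 5 leaving.

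**Front-loaded hazard, R = 50%, k = 2**

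- f = 0.5: 45.9%.
- f = 0.8: s = 1 − 0.5^0.8 = 42.6%, crude = (8 × 0.50 + 2 × 0.426)/10 = 48.5%, a relative shortfall of about 3%.
- f = 1: 50%, no shortfall.

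**Chance that at least one patient leaves**, 1 − (1 − p)^10: 65%, 89% or 97% if the non-response rate p is 10%, 20% or 30%.

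**Sampling error for comparison.** Exact 95% intervals are 19–81% for 5/10 and 3–56% for 2/10.

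**The case against.** The strongest reply is that this is a 10-patient exploratory trial with one arm and no decision rule based on adverse event percentages. No between-arm comparison can be biased. With 2 leaving and a 50% risk, the shift is 0.8 of a patient (5.0 against 4.2), far inside the interval around 5/10. All of that stands and limits the weight of the point. It does not settle which period the percentage describes.

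The plan also never calls the percentage a one-year risk. Stopping non-responders is part of the strategy under study, and the share of treated patients with an event under that strategy is a legitimate description if follow-up is stated beside it. That too stands, but 8.5.2 states no follow-up.

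The constant hazard may be wrong. The 300 mg dose comes first and visits are densest in the first month, so recorded events could well be concentrated early. The shortfall would then be small or nil.

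Late harm is not ignored. Section 6.2.1 has detected events followed to resolution and asks patients to report later events thought to be related, and 6.2.2 keeps suspected late serious events reportable. This covers related events, mainly serious ones, not all adverse events.

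Finally, with 10 patients a reader could set events against exposure from the listings. That is possible, but no such summary is planned.

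A reader might go further and infer that one-year harm is understated as a matter of fact, or that the crude percentage is meaningless. The documents support neither: they give no non-response rate and no timing of events, and with no Day 30 exits the shortfall is zero.

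**Conclusion.** The gap is real and conditional. Section 8.5.2 plans only crude numbers and percentages, follow-up differs about sixfold by design and according to response, and no section adjusts for it. Read as the safety of one year of treatment, the percentage can be too low. This requires at least one Day 30 exit and risk that continues beyond about Day 56.

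The relative shortfall is 0 with no exits. Under a constant hazard it is about 8% with one exit, 16–17% with two and 40–42% with five. With two exits and R = 50% it falls to about 3% if 80% of the hazard is early. These figures rest on assumed values of the one-year risk, the number leaving and the hazard shape, and on leavers having the same underlying risk as those who stay.

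The point merits a change in the analysis text because the remedy is cheap, although sampling error at 10 patients is larger than the likely shortfall.

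**What to change.** In section 8.5.2:

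1. Keep the crude counts and percentages, and print follow-up time (median, range and total patient-years) beside them.
2. Add adverse event tables for Day 0 to 30 (all dosed patients) and after Day 30 (patients who continue), each with its own denominator. List separately any events in dropped patients between Day 30 and their last assessment, so that none is lost. This split matters most, because it does not require leavers and continuers to share the same later risk.
3. Add the number of patients with a first event per patient-year, with exact 95% intervals. Count time from first dose to the first event or the last adverse event assessment. Do not use the exposure days of 8.3: they are undefined after a single dose and are not follow-up time. Use first events because repeat events within 10 patients are not independent and would make a Poisson interval too narrow. State that a pooled rate assumes dropped patients would have had the later risk of those who stay.
4. Reconcile the 8-week visit and the 30-day minimum contact in 5.7 with the 30-day serious event window in 6.2.2, so that the adverse event collection period, and hence the denominator, is defined.

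The cost is some wording and two extra tables from dates that should already be recorded. The downside is that their intervals will be wide at 10 patients. The design and the visits need not change for items 1 to 3.
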